8.6 Visit 6 (Week 8 ± 3 Days)

Set up the appropriate number of study drug vials to thaw in the refrigerator approximately 16 to 24 hours before scheduled study drug administration and according to [Section 6.1.2](#).

Complete the following procedures during the visit:

- Collect a urine sample for a urine pregnancy test for female subjects of childbearing potential and for urinalysis.
 - Any subject with a positive pregnancy test result must complete ET procedures and will be recorded as ET.
- Record any changes in concomitant medications since the previous visit.
- Record any new AEs that may have occurred since the previous visit and follow up on the status of any existing AEs.
- Obtain weight.
- Measure vital signs (blood pressure, heart rate, temperature, and respiratory rate) with subject in a sitting position after having rested for 5 minutes.
- Collect blood samples for clinical laboratory tests (chemistry and hematology).
- Collect pre-dose blood samples for serum PK and CSF1 (and anti-AMB-05X antibody, if the subject will be receiving the last dose of study drug at this visit).
- Optional assessment: If the subject will be receiving the **last** dose of study drug at this visit, collect pre-dose synovial fluid for PK, CSF1, and anti-AMB-05X antibody.
- Administer study drug via IV infusion to the affected joint.
- Collect post-dose blood samples for serum PK and CSF1 within 15 minutes after the end of infusion.
- Monitor the subject for at least 60 minutes post-dose for any adverse reactions, including any infusion-site reactions.
- Schedule the next visit with the subject.
- Contact IWRs to record the visit.

8.7 Visit 7 (Week 10 ± 3 Days)

If the subject is on an every-2-weeks study drug regimen, set up the appropriate number of study drug vials to thaw in the refrigerator approximately 16 to 24 hours before scheduled study drug administration and according to [Section 6.1.2](#).

For all subjects, complete the following procedures during the visit:

- Record any changes in concomitant medications since the previous visit.
- Record any new AEs that may have occurred since the previous visit and follow up on the status of any existing AEs.
- Obtain weight.
- Measure vital signs (blood pressure, heart rate, temperature, and respiratory rate) with subject in a sitting position after having rested for 5 minutes.
- Collect a urine sample for urinalysis.
- Collect blood samples for clinical laboratory tests (chemistry and hematology).
- Collect blood samples for serum PK and CSF1 (before study drug administration, if applicable for the subject).
- Schedule the next visit with the subject.
- Contact IWRS to record the visit.

If the subject is on an every-2-weeks study drug regimen (and thus will be receiving the **last** dose of study drug at this visit):

- Collect a pre-dose blood sample for serum anti-AMB-05X antibody.
- Optional assessment: collect synovial fluid for PK, CSF1, and anti-AMB-05X antibody.
- Administer study drug via IV infusion.
- Collect post-dose blood samples for serum PK and CSF1 within 15 minutes after the end of infusion.
- Monitor the subject for at least 60 minutes post-dose for any adverse reactions, including any infusion-site reactions.

8.8 Visit 8 (Week 12 ± 3 Days) or Early Termination

Complete the following procedures during the visit:

- Collect a urine sample for a urine pregnancy test for female subjects of childbearing potential and for urinalysis.
- Record any changes in concomitant medications since the previous visit.
- Record any new AEs that may have occurred since the previous visit and follow up on the status of any existing AEs.
- Obtain weight.
- Measure vital signs (blood pressure, heart rate, temperature, and respiratory rate) with subject in a sitting position after having rested for 5 minutes.
- Conduct a full physical examination and document any changes since the previous physical exam.
- Perform a 12-lead ECG.
- Evaluate ROM of the affected joint.

- Administer the following PRO instruments:
 - PROMIS Physical Function Scale
 - Worst Stiffness NRS
 - BPI Short Form
 - EQ-5D-5L
- Collect blood samples for clinical laboratory tests (chemistry and hematology).
- Collect blood samples for serum PK and CSF1.
- Perform MRI. A central radiologist will evaluate MRI scans to assess tumors.
- Schedule the next visit with the subject.
- Contact IWRs to record the visit.

8.9 Follow-up Visit 9 (Week 14 ± 3 Days)

- Record any changes in concomitant medications since the previous visit.
- Record any new AEs that may have occurred since the previous visit and follow up on the status of any existing AEs.
- Obtain weight.
- Measure vital signs (blood pressure, heart rate, temperature, and respiratory rate) with subject in a sitting position after having rested for 5 minutes.
- Conduct a full physical examination and document any changes since the previous visit.
- Evaluate ROM of the affected joint.
- Administer the Worst Stiffness NRS.
- Collect a urine sample for a urine pregnancy test for female subjects of childbearing potential and for urinalysis.
- Collect blood samples for clinical laboratory (chemistry and hematology).
- Collect blood samples for serum PK, CSF1, and anti-AMB-05X antibody.
- Schedule the next visit with the subject.
- Contact IWRs to record the visit.

8.10 Follow-up Visit 10 (Week 24 ± 7 Days)

- Record any changes in concomitant medications since the previous visit.
- Record any new AEs that may have occurred since the previous visit and follow up on the status of any existing AEs.
- Obtain weight.
- Measure vital signs (blood pressure, heart rate, temperature, and respiratory rate) with the subject in a sitting position after having rested for 5 minutes.
- Conduct a full physical examination and document any changes since the previous visit.

- Evaluate ROM of the affected joint.
- Administer the following PRO instruments:
 - PROMIS Physical Function Scale
 - Worst Stiffness NRS
 - BPI Short Form
 - EQ-5D-5L
- Collect a urine sample for a urine pregnancy test for female subjects of childbearing potential and for urinalysis.
- Collect blood samples for clinical laboratory tests (chemistry and hematology).
- Collect blood samples for serum PK and CSF1.
- Perform MRI. A central radiologist will evaluate MRI scans to assess tumors.
- Contact IWRS to record the visit.

8.11 Early Termination Procedures

A subject who terminates early from the study and does not withdraw consent for study participation will be asked to complete Visit 8 (Week 12) ([Section 8.8](#)), Visit 9 (Week 14) ([Section 8.9](#)), and Visit 10 (Week 24) ([Section 8.10](#)) (whichever visits the subject has yet to complete at the time of ET). Study personnel will make every effort to conduct all protocol-specified procedures to complete the study, including a final MRI.

9 STATISTICAL CONSIDERATIONS

9.1 Sample Size Determination

Based on prior Phase 1 experience and an anticipated treatment effect with AMB-05X in this population, the sample size of 3 to 12 subjects per cohort is anticipated to provide sufficient data for PK/PD analysis and an estimate of safety, tolerability, and efficacy.

9.2 Populations for Analyses

Safety Population: This population will include all subjects who receive at least 1 dose of study drug. The Safety Population will be used for analysis of safety data.

Modified Intent-To-Treat (mITT) Population: This population will include all subjects who receive at least 1 dose of study drug and have both baseline and post-baseline data for at least 1 efficacy endpoint. The mITT Population will be the primary analysis population for efficacy analysis.

Per-Protocol Population (PP): This population will include subjects in the mITT Population who complete the study and do not have protocol deviations that could significantly affect the interpretation of the endpoints. The PP Population will be identified before database lock. The PP Population may be used for sensitivity analyses of efficacy endpoints.

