3.2 Secondary Endpoints

3.2.1 Efficacy Secondary Endpoints

The following efficacy endpoints will be assessed at Week 12:

- Proportion of subjects who achieve an overall tumor response (OR, which includes both CR and PR) per RECIST v1.1 ([Eisenhauer, 2009](#))
- Proportion of subjects with overall response based on TVS, a TGCT-specific method that calculates tumor volume as a percentage of the estimated maximally distended synovial cavity
- Mean change from Baseline in ROM score
- Mean change from Baseline in the PROMIS Physical Function score
- Mean change from Baseline in Worst Stiffness NRS score
- Percentage of subjects who respond with a decrease of at least 30% in mean BPI score from Baseline
- Mean change from Baseline in BPI score
- Mean change from Baseline in Worst Pain NRS score
- Mean change from Baseline in EQ-5D-5L health assessment

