4.1.2 Adaptive Dose Cohorts and Data Monitoring Committee

The study will enroll up to approximately 48 subjects total into up to 6 serial dose cohorts, designated Cohorts A through F. Each cohort will be composed of at least 3 and at most 12 subjects. All subjects, regardless of their dose regimen, will have a study visit every 2 weeks during the treatment period.

Dosing will begin with Cohort A at the following starting dose level and regimen:

- An initial priming dose of 4 mg/kg on Day 1
- Followed by 5 maintenance doses of 2 mg/kg administered every 2 weeks (at Weeks 2, 4, 6, 8, and 10)

The dose levels and regimens for subsequent cohorts will be determined by the Sponsor based on an ongoing analysis of available data from the previous cohort(s). The following range of dose levels and regimens may be implemented in subsequent cohorts without a protocol amendment:

Range of Dose Levels		
	Initial Dose on Day 1	Maintenance Doses
Minimum	2 mg/kg	1 mg/kg
Maximum	12 mg/kg	8 mg/kg

Although the minimum and maximum specified for the initial dose are both higher than those specified for maintenance doses, the initial dose does not have to be higher than subsequent maintenance doses. While remaining within the range specified, the initial dose may be the same as the subsequent maintenance doses, or the initial dose may be a higher, priming dose.

Allowable Regimens			
	Frequency	# Doses	Schedule
Minimum	Every 4 weeks	3 doses	Initial dose on Day 1
			2 maintenance doses, at Weeks 4, 8
Maximum	Every 2 weeks	6 doses	Initial dose on Day 1
			5 maintenance doses, at Weeks 2, 4, 6, 8, 10

Thus, the lowest dose that a cohort could receive would be an initial dose of 2 mg/kg on Day 1, followed by 2 maintenance doses of 1 mg/kg every 4 weeks (at Weeks 4 and 8). The highest dose that a cohort could receive would be an initial dose of 12 mg/kg on Day 1, followed by 5 maintenance doses of 8 mg/kg every 2 weeks (at Weeks 2, 4, 6, 8, and 10).

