- If ≥ 3 subjects in a 3- or 6-subject cohort experience a clinically significant AE, the Sponsor will suspend dosing and enrollment in that cohort and/or any further dose escalation in the study. Additional subjects may be enrolled at a lower dose.
- If data from the first 3 subjects in a cohort to complete treatment indicate suboptimal drug exposure and efficacy, and there are no significant safety issues such as clinically significant AEs, the Sponsor may elect to discontinue further enrollment in that cohort and proceed directly to the next cohort.
- If safety permits according to the rules above (ie, if $\leq 1/3$ of the previous subjects in the cohort experience a clinically significant AE), the Sponsor may elect to enroll up to 12 subjects per cohort for more conclusive data.
- Following the rules above, the Sponsor may elect to enroll the subsequent cohort in a staggered / overlapping manner (initiating enrollment in the next cohort while the current cohort is still completing the study or still enrolling) or sequentially (waiting until more complete data are available from the current cohort before initiating the next cohort).
- The Sponsor may discontinue further enrollment and/or suspend/terminate the study (see [Section 10.1.7](#)).

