9.3.2 Handling Missing Data

All available data will be presented as descriptive summaries or listings. Missing data will not be imputed.

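### No efficacy analysis in the supplied text covers all treated subjects; an all-treated Week 12 tumor response rate should stand beside the mITT rate (minor)

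*Combined protocol and SAP*

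**What the plan says.** Section 9.2 admits to mITT the dosed subjects who "have both baseline and post-baseline data for at least 1 efficacy endpoint", and gives the set its role: "The mITT Population will be the primary analysis population for efficacy analysis". The per-protocol set is drawn from mITT and further limited to subjects who finish the study without important deviations. Its use is optional: "The PP Population may be used for sensitivity analyses of efficacy endpoints". The Safety Population, which holds everyone dosed, is assigned to safety data.

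On missing values Section 9.3.2 says "Missing data will not be imputed", with no exception for responder endpoints. The tumor endpoints in Section 3.2.1 are Week 12 proportions, for example "Proportion of subjects who achieve an overall tumor response" by RECIST v1.1, and the corresponding rate by tumor volume score (TVS). Section 9.3.1 has results summarized by dose cohort and overall, and Section 4.1.2 sets the cohort size: "Each cohort will be composed of at least 3 and at most 12 subjects".

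Sections 8.3 and 8.4 list no MRI, range of motion or patient-reported outcome at Weeks 2 and 4. The first scheduled efficacy data after dosing come at Week 6 (Section 8.5).

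**The concern.** Membership of the primary efficacy set depends on something that happens after treatment starts. A subject who is dosed on Day 1, then withdraws consent or is lost before Week 6, has no post-baseline efficacy data and is not counted. Section 4.4 names adverse events, lack of efficacy and loss to follow-up among the reasons for stopping, so such exits need not be unrelated to outcome.

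The one named sensitivity set moves further from the treated population, not closer to it. The response rates have no concurrent control, so the choice of denominator acts directly on the figure that is reported. In a cohort of 3, a single exclusion could turn 2 of 3 into 2 of 2.

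**Working it through.** The plan has no figure of its own to reproduce. Section 9.1 gives 3 to 12 subjects per cohort with no assumed response rate, drop-out rate or precision target.

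**Inputs**
- n, treated subjects: 3 to 12 per cohort, up to about 48 in total (Section 4.1.2).
- p, response rate: assumed 39% to 86%. These are the rates that Section 2.1 reports for two other CSF1R inhibitors in this disease.
- d, share of treated subjects excluded from mITT: not given. Assumed 2% to 16%. The top value is the rate of withdrawal for adverse events in the first-in-human study in advanced solid tumors (Section 2.4.1), and is probably too high here.

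**Step 1: effect of one exclusion.** With r responders and one excluded subject counted as a non-responder, the all-treated rate is r/n and the mITT rate is r/(n-1). The ratio is n/(n-1). The difference is r/[n(n-1)], which is largest at r = n-1, where it equals 1/n.

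| n | Factor | Largest shift (points) | Example near 39% | Example near 86% |
|---|---|---|---|---|
| 3 | 1.50 | 33.3 | 1/3 = 33.3% vs 1/2 = 50.0% | 2/3 = 66.7% vs 2/2 = 100% |
| 6 | 1.20 | 16.7 | 2/6 = 33.3% vs 2/5 = 40.0% | 5/6 = 83.3% vs 5/5 = 100% |
| 12 | 1.09 | 8.3 | 5/12 = 41.7% vs 5/11 = 45.5% | 10/12 = 83.3% vs 10/11 = 90.9% |
| 48 | 1.02 | 2.1 | 19/48 = 39.6% vs 19/47 = 40.4% | 41/48 = 85.4% vs 41/47 = 87.2% |

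Exact (Clopper-Pearson) 95% intervals overlap heavily. For 1/3 against 1/2 they are 0.8-90.6% and 1.3-98.7%. For 2/3 against 2/2 they are 9.4-99.2% and 15.8-100%. For 10/12 against 10/11 they are 51.6-97.9% and 58.7-99.8%.

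**Step 2: chance that a cohort has any exclusion**, 1-(1-d)^n:

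| d (assumed) | n=3 | n=6 | n=12 |
|---|---|---|---|
| 2% | 5.9% | 11.4% | 21.5% |
| 5% | 14.3% | 26.5% | 46.0% |
| 16% | 40.7% | 64.9% | 87.7% |

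**Step 3: expected shift.** If p is the response rate among retained subjects, the mITT rate has expectation p and the all-treated rate p(1-d). The shift is p × d, with no n in it. For p from 39% to 86% this gives 0.8 to 1.7 points at d = 2%, 2.0 to 4.3 at 5%, and 6.2 to 13.8 at 16%. A small cohort takes a larger shift per exclusion but is less likely to have one, and the two offset.

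**The case against.** The strongest reply is that little turns on this.

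- The excluded group is narrow. Any one efficacy endpoint is enough for entry to mITT, and early terminators who keep consent are asked to complete Visits 8 to 10, with a final MRI (Sections 4.4 and 8.11).
- The primary endpoint, treatment-emergent adverse events, uses everyone dosed.
- The cohort rule for poor efficacy is worded around treatment completers ("If data from the first 3 subjects in a cohort to complete treatment indicate suboptimal drug exposure and efficacy"), so it does not use the mITT rate.
- Baseline tables use the Safety Population (Section 9.3.3), so a reader can rebuild the all-treated point estimate from the responder count.

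All of this stands, and it keeps the point minor. It does not supply the missing analysis: the supplied text commits to neither the all-treated rate with its interval nor a count of missing responses.

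A reader might also infer more than the documents support:

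- *That the trial will have no all-treated response rate.* Section 9.3.1 announces a separate detailed analysis plan, which could contain one. It could also settle how a subject with Week 6 but no Week 12 data is counted, which the supplied text leaves undefined.
- *That the problem grows as cohorts shrink.* This is true per excluded subject, but not of the expected shift (Step 3).
- *That the mITT rate overstates the true response rate.* It equals or exceeds the all-treated rate because missing is counted as non-response there. That follows from the benchmark and shows no bias against the truth.
- *That mITT should lose its primary role, or that the same rule should cover the pain responder endpoint.* Neither follows from the gap. Section 5.1 requires no baseline pain, and a score of 0 cannot fall by 30%, so that endpoint's denominator is a separate question.

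**Conclusion.** The point holds as a minor gap in the supplied text. Treated subjects without post-baseline efficacy data leave the efficacy analyses, and no stated analysis brings them back.

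Per exclusion the response rate is multiplied by 1.50, 1.20, 1.09 or 1.02 at n = 3, 6, 12 or 48, a shift of at most 1/n. These figures assume that exactly one subject is excluded and is counted as a non-responder in the comparison rate; with no exclusions there is no effect. The expected shift cannot be sized from the documents, and the ranges in Step 3 rest on assumed exclusion and response rates.

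The figures measure the mITT entry rule alone. They do not measure the further effect of counting mITT members with no Week 12 scan as non-responders.

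**What to change.** Add to Sections 9.2 and 9.3.2, or to the separate analysis plan: Week 12 RECIST and TVS response rates with 95% confidence intervals are also reported on all treated subjects, by cohort and overall, with a missing or non-evaluable Week 12 response counted as non-response. Show this beside the mITT observed-case rate, with the number missing in each cohort. The mITT set keeps its present role.

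The cost is a sentence or two and no new data. A protocol edit would need the approvals in Section 10.1.6. An entry in the analysis plan is lighter, but should say that this rule is a stated exception to the ban on imputation.

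The downside is that the all-treated rate may be slightly less favorable, and that it treats unrelated missingness, such as a scan lost to COVID-19 restrictions (Appendix 5), as non-response. The mITT rate and the missing count beside it show how much that matters.

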9.3 Statistical Analyses

9.3.1 General Approach

All study data will be summarized by dose cohort and overall using descriptive statistics. Data from all investigational centers will be pooled for analyses. Unless otherwise specified, descriptive statistics for numeric data (eg, age, weight) will include the number of subjects with data to be summarized (n), mean, SD, median, minimum, and maximum. Categorical/qualitative data (eg, sex, race) will be presented using absolute and relative frequency counts and percentages. All summaries, statistical analyses, and individual subject data listings will be completed using SAS software (SAS Institute, Inc; Cary, North Carolina) Version 9.3 or later.

A detailed statistical analysis plan will be finalized before the first DMC meeting and will be provided separately.

9.3.2 Handling Missing Data

All available data will be presented as descriptive summaries or listings. Missing data will not be imputed.

9.3.3 Demographics and Baseline Characteristics

Demographics and baseline characteristics will be summarized descriptively for the Safety Population.

9.3.4 Safety Analyses

Safety analyses will include all subjects who receive at least 1 dose of study drug.

The number of subjects exposed to study drug and the duration of exposure will be summarized.

All AEs reported will be listed, documenting severity, start and stop date and time, possible relationship to study drug, action taken, and outcome. TEAEs are defined as AEs that occur after the first dose of study drug. Verbatim terms will be mapped to PTs and related SOCs using MedDRA. PTs and SOCs will be tabulated by dose cohort and overall. All reported AEs will be summarized by the number of subjects reporting each AE, SOC, PT, severity, and relationship to study drug. Multiple occurrences of an AE will be counted only once per subject per SOC and PT in summary tables.

The following will be summarized by SOC, PT, and dose cohort:

- Incidence of all TEAEs
- Incidence of all TEAEs by maximum severity (severe, moderate, and mild) specified by investigators
- Incidence of TEAEs related to study drug as determined by investigators
- Incidence of serious TEAEs
- Incidence of TEAEs leading to early discontinuation/withdrawal from the study

Safety labs (including hematology, chemistry, and urinalysis), vital signs, and ECGs will be tabulated using descriptive statistics. Abnormal/out-of-range findings and changes from pre-dose to post-dose will be listed by subject. Safety labs will be displayed graphically. Shift tables will be provided for all laboratory variables. For ECG parameters, heart rate, RR, PR, QRS, and QTcF will be summarized.

Concomitant medication usage will be summarized. The World Health Organization Drug Dictionary will be used to classify concomitant medications by therapeutic class and generic name based on ATC (Anatomical Therapeutic Chemical) code level 3. A subject will only be counted once in each unique ATC class and generic name if the subject uses multiple drugs.

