	
anticipated to provide sufficient data for PK/PD analysis and an estimate of safety, tolerability, and efficacy.
 
Analysis Methods
 
All study data will be summarized by dose cohort and overall using descriptive statistics.
 
Safety Analyses
 
Safety analyses will include all subjects who receive at least 1 dose of study drug.
 
All AEs reported will be listed, documenting severity, start and stop date and time, possible relationship to study drug, action taken, and outcome. TEAEs are defined as AEs that occur after the first dose of study drug. Verbatim terms will be mapped to Preferred Terms (PTs) and related System Organ Classes (SOCs) using the Medical Dictionary for Regulatory Activities (MedDRA). PTs and SOCs will be tabulated by dose cohort and overall. All reported AEs will be summarized by the number of subjects reporting each AE, SOC, PT, severity, and relationship to study drug. Multiple occurrences of an AE will be counted only once per subject per SOC and PT in summary tables.
 
Safety labs (including hematology, chemistry, and urinalysis), vital signs, tolerability data, and ECGs will be tabulated using descriptive statistics. Abnormal/out-of-range findings and changes from pre-dose to post-dose will be listed by subject. Shift tables will be provided for all laboratory variables.
 
Efficacy Analyses
 
Efficacy endpoints will be summarized using descriptive statistics and 95% confidence intervals. Exploratory hypotheses testing may be conducted using a significance level of 0.05 without adjustment for multiplicity.
 
Pharmacokinetic Analyses
 
AMB-05X concentrations will be summarized by dose, regimen, and nominal collection time. If warranted, a population PK analysis may be conducted using data from the current study and relevant data from other clinical studies. In addition, an exposure-response analysis may be attempted using the population approach.

--	--

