2.4.1 Monotherapy Study

The first-in-human study of IV AMB-05X evaluated safety, tolerability, PK, and PD in subjects with advanced solid tumors (Papadopoulos, 2017). The study initially dosed subjects once weekly at 0.5 mg/kg. In subsequent cohorts, the dosing regimen was revised to IV infusion over a 60-minute period every 2 weeks. Escalation of AMB-05X dose was advanced through 1.5, 3, 6, 10, and 20 mg/kg levels.

All 25 subjects (100%) had measurable disease at baseline by local assessment, which supported their enrollment into the study. By central assessment, 21 subjects (84%) had measurable disease at baseline. Per central assessment, 8 subjects (32%) had a best response of stable disease; per local assessment, 1 subject (4.0%) had partial response and 6 subjects (24%) had stable disease (central and local assessments of subject response did not fully overlap). Per central assessment, 1 subject (with stable disease) had a >20% reduction in tumor burden based on RECIST; per local assessment, 1 subject (with partial response) had a 40% reduction in tumor burden. The median for maximum percentage change from baseline in tumor volume was 19.3% (range: -24.0% to 104.8%).

All 25 subjects (100%) had at least 1 TEAE; the most common were nausea and vomiting (12 subjects [48%] each); fatigue and periorbital edema (11 subjects [44%] each); constipation (9 subjects [36%]); and anemia, AST increased, and decreased appetite (8 subjects [32%] each). A total of 18 subjects (72%) had AEs that were at least Grade 3 in severity and 5 (20%) had AEs that were at least Grade 4.

One subject in the 20-mg/kg cohort experienced a nonreversible DLT of Grade 3 bilateral deafness; lack of a baseline audiology exam and the recent receipt of multiple cycles of cisplatin therapy (1 month before first dose of AMB-05X) precluded any meaningful assessment of the progressive aspect of hearing loss.

SAEs were reported for 11 subjects (44%), AEs leading to withdrawal from the study were reported for 4 subjects (16%), and AEs leading to discontinuation of investigational product were

reported for 5 subjects (20%). Fatal AEs were reported for 3 subjects (12%); the events occurred in the setting of progressive disease and were considered not related to treatment with AMB-05X by the investigators.

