3.1 Primary Endpoint

The primary endpoint is the frequency and severity of reported TEAEs.

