7.3.3 Classification of an Adverse Event

7.3.3.1 Severity

The Investigator will provide an assessment of the severity of each AE by recording a severity rating on the AE page of the subject's eCRF. Severity, which is a description of the intensity of manifestation of the AE, is distinct from seriousness. Severity will be graded according to the National Cancer Institute Common Terminology Criteria for Adverse Events (CTCAE) version 5.0 ([CTCAE 2017](#)), summarized here:

- **Grade 1:** Mild; asymptomatic or mild symptoms; clinical or diagnostic observations only; intervention not indicated.
- **Grade 2:** Moderate; minimal, local, or noninvasive intervention indicated; limiting age-appropriate instrumental activities of daily living (preparing meals, shopping for groceries or clothes, using the telephone, managing money, etc).
- **Grade 3:** Severe or medically significant but not immediately life-threatening; hospitalization or prolongation of hospitalization indicated; disabling; limiting self-care activities of daily living (bathing, dressing and undressing, feeding self, using the toilet, taking medications, and not bedridden).
- **Grade 4:** Life-threatening consequences; urgent intervention indicated.
- **Grade 5:** Death related to AE.

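### The TEAE severity table has three levels (mild, moderate, severe) but investigators record CTCAE Grades 1 to 5, so Grades 4 and 5 have no stated place in it

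*Combined protocol and SAP*

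**What the plan says.** Section 3.1 defines the primary outcome: "The primary endpoint is the frequency and severity of reported TEAEs".

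Section 7.3.3.1 sets the scale that investigators use: "Severity will be graded according to the National Cancer Institute Common Terminology Criteria for Adverse Events (CTCAE) version 5.0". Its summary of the grades labels Grade 1 as mild and Grade 2 as moderate. Grade 3 is "Severe or medically significant but not immediately life-threatening", Grade 4 is "Life-threatening consequences; urgent intervention indicated", and Grade 5 is death related to the AE.

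Section 9.3.4 then lists the TEAE tables to be produced by SOC, PT and dose cohort. The severity table is "Incidence of all TEAEs by maximum severity (severe, moderate, and mild) specified by investigators".

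One other severity summary is planned, in the same words in the synopsis (section 1.1) and in section 9.3.4: "All reported AEs will be summarized by the number of subjects reporting each AE, SOC, PT, severity, and relationship to study drug". It names no levels. Section 9.3.1 adds: "A detailed statistical analysis plan will be finalized before the first DMC meeting and will be provided separately". That separate plan is not part of the documents available.

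**The concern.** The table is said to show what investigators specified, but investigators specify one of five grades and the table has three levels. The protocol's own definitions do not let severe absorb the top two grades without comment, because Grade 3 is defined by not being immediately life-threatening and Grade 4 by being so.

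Two programmers could both follow the text and produce different tables. One would leave Grade 4 and 5 events without a row; the other would pool them with Grade 3. Either way, the only severity table with named levels could not show, by cohort, whether a subject's worst event was Grade 3, life-threatening or fatal. In a dose-escalation study with severity in its primary endpoint, that distinction is basic.

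**Working it through.** **1. The two scales side by side**

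| Recorded grade (section 7.3.3.1) | Protocol's label | Matching level in the section 9.3.4 table |
|---|---|---|
| 1 | Mild | Mild |
| 2 | Moderate | Moderate |
| 3 | Severe, not immediately life-threatening | Severe |
| 4 | Life-threatening | None named |
| 5 | Death | None named |

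Five recorded levels meet three tabulated ones. Three match by label and two do not.

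**2. Search for a mapping or another graded table**

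- The general AE summary (synopsis and section 9.3.4) uses the word severity without categories.
- The AE listing shows severity event by event, but it is not a summary by cohort.
- The serious-TEAE table is by SOC, PT and cohort, with no grade breakdown.
- The DLT definition (sections 4.1.2 and 7.3.8.1) uses Grade 3 or higher, so grades are the working currency elsewhere, but it gives no mapping to mild, moderate and severe.

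No mapping was found. The plan states no figure that needs reproducing on this point.

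**3. How much a pooled row could hide: illustration from the monotherapy study**

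Input (section 2.4.1, 25 subjects): "18 subjects (72%) had AEs that were at least Grade 3 in severity and 5 (20%) had AEs that were at least Grade 4". These counts are cumulative.

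- Maximum grade exactly 3: 18 − 5 = 13, and 13/25 = 52%.
- Maximum grade 4 or 5: 5/25 = 20% (Clopper-Pearson 95% CI 6.8% to 40.7%).
- Share of a pooled severe row that is Grade 4 or 5: 5/18 = 27.8%.

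Under the literal reading, those 5 subjects' Grade 4 or 5 events would have no row. These are all-cause AEs in advanced solid tumors, so the rate does not carry over to TGCT.

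**4. How likely the situation is to arise here**

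The documents give no Grade 4 or higher rate for TGCT, so the rate p below is an assumption. For n subjects, P(at least one subject with a Grade 4 or higher TEAE) = 1 − (1 − p)^n. Cohorts hold 3 to 12 subjects, and the study up to about 48.

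| Assumed p | n = 3 | n = 12 | n = 48 |
|---|---|---|---|
| 1% | 3% | 11% | 38% |
| 2% | 6% | 22% | 62% |
| 5% | 14% | 46% | 91% |
| 10% | 27% | 72% | 99% |

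For example, p = 5% and n = 12 gives 1 − 0.95^12 = 0.460. At full enrollment, the table would more likely than not meet at least one such subject once p is about 2%. In a cohort of 3, it usually would not.

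**The case against.** The strongest reply is that this is a loose parenthetical in one bullet, and that the information will be reported anyway.

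- **The general severity summary may be by grade.** Section 7.3.3.1 ties severity to CTCAE, and section 9.3.1 has all data summarized by cohort and overall, so reading it as a by-cohort CTCAE summary is reasonable. This stands as a possibility. It does not remove the conflict, because the one table that names its levels names the wrong ones.
- **Serious events are tabulated separately.** Death and life-threatening events meet the seriousness criteria in section 7.3.2, so fatal events will appear in the serious-TEAE table and Grade 4 events generally should. This narrows the gap. That table still mixes them with events that are serious for other reasons, such as hospitalization, and does not show grade.
- **No decision turns on it.** Grades 3, 4 and 5 count alike toward a DLT when at least possibly related, nothing ties the DMC's review to this table, and the primary endpoint is summarized descriptively. All of this stands; the point concerns reporting only.
- **The separate SAP may settle it.** It may. If it tabulates Grades 1 to 5, the protocol bullet still disagrees with it and needs aligning.
- **The illustration comes from a sicker population.** This is correct. The 20% and 28% show what pooling can conceal, and should not be read as expected rates.

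**Conclusion.** The concern holds. The severity table in section 9.3.4 is wrong as written, because its levels conflict with the scale that section 7.3.3.1 requires for a component of the primary endpoint. The finding rests on the text alone and needs no assumption about event rates.

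Its size is moderate. Grades are recorded in full, so nothing is lost that a corrected table cannot recover, and sample size, error rates, analysis populations and escalation rules are unaffected. What remains open is whether the general severity summary or the separate SAP already uses the five grades. The change should be made, but it does not put the study's validity in doubt.

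**What to change.** Reword the bullet in section 9.3.4 to incidence of all TEAEs by maximum CTCAE v5.0 grade (1, 2, 3, 4, 5). Use the same five levels for the general severity summary in section 9.3.4 and the synopsis, and check that the separate SAP agrees. A Grade 3 or higher subtotal is a useful addition, since the DLT definition uses that threshold, but the correction does not depend on it.

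If three levels are kept for any reason, state the mapping from Grades 1 to 5 and show Grades 4 and 5 as separate sub-rows.

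The cost is one reworded bullet, matching wording for the general summary, and two extra severity rows plus the optional subtotal. No new data are needed, because the grade is already recorded for every AE.
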